## 11 Safety Analyses

All safety analyses will be based on the SAF as defined in Section 6.

### 11.1 Responder (Primary Endpoint)

For each cohort the percentage of responders will be calculated for each infusion parameter level. The infusion parameter levels per cohort are displayed in Table 1.

**Table 1: Infusion parameter levels per cohort**

Cohort (c)	Infusion Parameter Levels (p)
Pump-Assisted Volume Cohort	Planned maximum volume per injection site 
 
• 25 mL
 
• 40 mL
 
• 50 mL
 

Cohort (c)	Infusion Parameter Levels (p)
Pump-Assisted Flow Rate Cohort	Planned maximum flow rate per injection site 
 
• 25 mL/h
 
• 50 mL/h
 
• 75 mL/h
 
• 100 mL/h
 

Manual Push Flow Rate Cohort	Planned flow rate per injection site 
 
• 30 mL/h [0.5 mL/min]
 
• 60 mL/h [1 mL/min]
 
• 120 mL/h [2 mL/min]
 

The definition of responder is based on the definition of valid infusions. Both definitions are provided in the following.

**Definition of valid infusions**

An infusion will be considered ‘valid’ if the subject completes the full dose per scheduled infusion parameter (volume or flow rate) under test without interruptions or decrease during that infusion. [Table 2](#) specifies for each cohort when an infusion is considered valid.

**Table 2: Minimum criteria for a valid infusion**

Pump-Assisted Volume Cohort		
Infusion Parameter	Definition Per Protocol	Modified Definition
Volume	Maximum volume administered per injection site is at least 95% of the planned max volume (i.e., 25 mL, 40 mL or 50 mL) for at least 1 injection site.	No modification
Flow rate	Not applicable	Not applicable
Dose	Total dose administered is at least 95% of the planned dose.	No modification

Pump-Assisted Volume Cohort		
Interruptions or stops	Not interrupted or stopped prematurely for any reason as documented in the eDiary.	May be stopped for technical reasons* only.
AEs	Not addressed.	No related AEs started during interrupted or stopped infusion.
*Technical reason: technical problem with any part of equipment (pump, syringe, tubing, needle, including needle placement) used for infusion.		

Pump-Assisted Flow Rate Cohort		
Infusion Parameter	Definition Per Protocol	Modified Definition
Volume	Not applicable	Not applicable
Flow rate	Injection site flow rate is at least 95% of the planned flow rate (i.e., 25 mL/h, 50 mL/h, 75 mL/h, or 100 mL/h) for at least one injection site.	No modification
Dose	Total dose administered is at least 95% of the planned dose.	No modification
Interruptions or stops	Not interrupted or stopped prematurely for any reason as documented in the eDiary.	May be stopped for technical reasons* only.
AEs	Not addressed.	No related AEs started during interrupted or stopped infusion.
*Technical reason: technical problem with any part of equipment (pump, syringe, tubing, needle, including needle placement) used for infusion.		

Manual Push Flow Rate Cohort		
Infusion Parameter	Definition Per Protocol	Modified Definition
Volume	The actual infusion volume is at least 95% of the planned infusion volume for that infusion day.	No modification
Flow rate	The actual infusion duration is not more than 1 minute or 10% (whichever is larger) longer than the calculated infusion duration based on the desired flow rate (i.e., 0.5 mL/minute, 1 mL/minute, or 2 mL/minute) and the actual volume infused.	No modification

Any deviation from the above defined criteria for each infusion parameter step will be considered a ‘failure’ (i.e. invalid infusion) in the analysis of this set of infusion parameters. However, if it is conducted as stated in the protocol but at a lower parameter level, it can be evaluated for the actual parameter as conducted. For example, if a subject was scheduled to a test volume of 50 mL/injection site, but for some reasons tested 45 mL/injection site, it will not count for the 50 mL level, but if that infusion was otherwise uneventful and performed in full without interruption, it will be considered valid for the 45 mL/injection site level, even though it was not planned. These unplanned parameter levels will be summarized in a separate column “Other” in the tables depending on the scenario. The data may not be summarized if the unplanned level only occurs in one subject. If all subjects have the same unplanned infusion parameter level, a column labelled with this unplanned level will be added. This unplanned column will not be included in the table shell but will only be inserted into the table output as necessary.

Protocol deviations may result in an invalid infusion even if there is adherence to the criteria as stated in [Table 2](#). The following protocol deviations will lead to invalidation of an infusion (this will have no impact on the assignment of a subject to the analysis sets):

- Prohibited concomitant medication
  - Any medications with the primary purpose of masking local or systemic AEs (including but not limited to analgesics and anesthetics  $\pm$  12h around the infusion).
  - Any Ig product other than the study medication

These protocol deviations will be assessed on an infusion basis, not on a subject basis. Prior to DB lock, the infusion data will be merged with the concomitant medication data so that the start date of an infusion can be compared with the start date of concomitant medication. This list will be provided to CSL as an Excel file. CSL will manually review this file and flag the infusions which will have to be considered invalid due to prohibited concomitant medication. Only concomitant medication with complete start dates can be considered in the merge to infusion data.

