7.2 Permitted Therapies

The following therapies are PERMITTED during the study:

- Any medications that do not have the primary purpose of masking local or systemic AEs, and that are taken by the subject on a regular basis.
- Prescribed medications required for the management of chronic medical conditions
- Over the counter medications and dietary supplements.

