7.3 Prohibited Therapies

The following therapies are NOT PERMITTED during the study:

- Any immunoglobulins other than IgPro20 provided for the study.
- Any other investigational product at any time during the study.
- Any medications with the primary purpose of masking local or systemic AEs (including but not limited to analgesics and anesthetics +/-12h around the infusion).
- Any systemic immunosuppressants that can affect serum IgG concentration (except for stable steroid doses required for pre-existing conditions).

Subjects are not to be enrolled into the study if they receive any prohibited therapy or any therapy in a prohibited dosage that cannot be discontinued or reduced to a permitted dose before enrollment.

If administration of any prohibited therapy becomes necessary during the study for medical reasons, the subject may be withdrawn from further study participation.

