#### **4.4 Randomization Procedures and Blinding**

This study is open-label and not randomized. Each study cohort requires specific entry criteria. However, these criteria are not mutually exclusive, and if a subject qualifies to be enrolled into more than one of the study cohorts, he/she may be assigned to either cohort at the investigator's discretion.

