#### **4.6 Planned Interim Analyses and Reviews**

##### **4.6.1 Interim Analyses Other Than Sample Size Re-estimation**

No formal interim analysis will be performed. Safety and IgG data will be examined by the study team in an ongoing fashion while the study is being conducted.

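### Infusions are ruled invalid for prohibited medication by the sponsor's manual review, with no decision rule or masking stated, and the ruling can settle a level that sits at the minimum number of responders

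*SAP*

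**What the plan says.** SAP 11.1 (Definition of valid infusions) and the definitions in SAP 2.2 make the absence of prohibited medication a condition for a valid infusion, even when volume, rate and dose criteria are met. Before lock, "the infusion data will be merged with the concomitant medication data" so that start dates can be compared. The result goes to the sponsor as a spreadsheet, and "CSL will manually review this file and flag the infusions which will have to be considered invalid due to prohibited concomitant medication". One limit is stated: "Only concomitant medication with complete start dates can be considered in the merge to infusion data".

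The SAP's list of invalidating medication repeats two items of Protocol 7.3: other immunoglobulins, and "Any medications with the primary purpose of masking local or systemic AEs (including but not limited to analgesics and anesthetics +/-12h around the infusion"). Protocol 7.2 permits, without qualification, "Over the counter medications and dietary supplements".

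On what the sponsor knows at that point, SAP 4.4 states that "This study is open-label and not randomized", and SAP 4.6.1 that "Safety and IgG data will be examined by the study team in an ongoing fashion while the study is being conducted".

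Valid infusions feed the primary endpoint. A pump-cohort subject responds at a level with at least 3 valid infusions of 4; a manual push subject needs at least k (SAP Table 3). A level succeeds at 33% or more of the cohort's safety set, and the highest successful level is the one to be recommended for the label (Protocol 11.3.5, SAP 11.1).

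**The concern.** The decision is discretionary, it is taken by the party with an interest in the result, and it acts on the primary endpoint.

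Discretion enters in two ways. First, the listed item turns on whether masking adverse events was the drug's main purpose. The parenthesis naming analgesics can be read as covering every analgesic in the window, or only those taken to mask. Second, an over-the-counter analgesic taken 6 h after an infusion falls under both Protocol 7.2 and 7.3, and neither document says which prevails. Such use is plausible, because local reactions are among the events under study.

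Protocol 14.4 left the full details of validation failure to the SAP. For medication the SAP gives a two-item list and a manual review, with no coded drug list, second reader, record of reasons or masking. Even if every decision is fair, the plan contains no analysis showing whether those decisions determined a label level.

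**Working it through.** **Inputs.** 15 evaluable subjects per cohort and a 50% assumed response rate (Protocol 11.1, SAP 4.5); success at 33% or more, given as 5 of 15 in Protocol 3.1; at least 3 valid of 4 in pump cohorts; 61% validity per infusion (Protocol 11.3.5, SAP 11.1). Subjects, and infusions within a subject, are treated as independent.

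**1. The plan's own figures.** P(X ≥ 5 | n = 15, p = 0.5) = 0.9408, which reproduces the stated 94%. P(at least 3 of 4 | 0.61) = 0.4925; 0.6143 gives 0.500, so 61% is a rounding of the value behind 50%.

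**2. One subject crosses the line.** 5/15 = 33.3% passes; 4/15 = 26.7% fails. With about 50 enrolled, cohorts may be slightly larger. The result is the same:

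| n | Minimum responders | One fewer | P(exactly the minimum) at 50% |
|---|---|---|---|
| 15 | 5 (33.3%) | 26.7% | 9.2% |
| 16 | 6 (37.5%) | 31.3% | 12.2% |
| 17 | 6 (35.3%) | 29.4% | 9.4% |
| 18 | 6 (33.3%) | 27.8% | 7.1% |

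**3. How often a level sits there.** P(X = 5 | 15, p) = C(15,5) p^5 (1−p)^10. At p = 0.50 this is 3003/32768 = 9.2%; at 0.40, 18.6%; at 0.33, 21.4%. These are per level. The plan has ten levels (3 + 4 + 3), and levels within a cohort share subjects, so the figures should not be added or multiplied.

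**4. Flags needed to remove a pump responder.** A subject with 4 valid infusions needs two flags (4 to 2). A subject with exactly 3 needs one (3 to 2). At 61% validity:

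- P(exactly 3) = 4 × 0.61³ × 0.39 = 0.3541
- P(4) = 0.61⁴ = 0.1385
- Share of responders with exactly 3 = 0.3541 / 0.4925 = 0.72

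Among five responders, the chance that at least one has exactly 3 is 1 − 0.28⁵ = 0.998. A level at exactly 5/15 is therefore almost always open to a single flag, if a disputed medication falls on one of that subject's valid infusions. The documents do not say how often that will happen.

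**5. Manual push.** At 61% validity, 26% to 45% of responders sit exactly at k, depending on schedule. A subject with every infusion valid is much harder to move: 8 − 5 + 1 = 4 flags at two infusions per week, and 28 − 17 + 1 = 12 at seven.

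**6. Strict against lenient reading (assumption).** Suppose a strict reading flags 5%, 10% or 20% of otherwise valid pump infusions that a lenient one leaves alone, independently. Per-infusion validity falls from 0.6143 to 0.6143 × (1 − f). The response rate falls from 50% to 45%, 40% or 30%, and the chance of passing falls from 94% to 87%, 77% or 48%.

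**The case against.** The strongest reply is that the SAP does give one operative list, taken from Protocol 7.3, and that analgesics within 12 h are named in it. Protocol 7.3 is more specific than 7.2, and the first bullet of 7.2 itself leaves out drugs meant to mask adverse events. The review precedes database lock, the procedure is pre-specified, and the study is descriptive. The listings give traceability: SAP 11.1 lists prohibited medication, validity and responder status by infusion, and SAP 9.4 lists each medication with dates, times and primary indication. A level sits exactly at the minimum only about 9% of the time at the planned rate. The label incentive would favour leaving doubtful infusions unflagged, not failing a level.

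Much of this stands. The conflict between 7.2 and 7.3 is an overlap, not two rival rules for the flag, and reading 7.3 as prevailing is reasonable. The listings would let a reader with access recompute the result. What remains is that precedence is not written, purpose still needs judgement, and timing before lock prevents later changes but does not mask the reviewer. The planned listings, as described, carry no reasons for a flag. The direction of the incentive does not matter: if the count is 5 with a disputed infusion left valid and 4 with it flagged, leaving it unflagged decides the level just as flagging it does.

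A reader might infer that the reviewer sees the outcome. The documents do not establish this. The file's columns are unspecified: it holds infusion data, and nothing says that validity or responder status is shown. Nothing says they are withheld either.

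**Conclusion.** The concern holds as a weakness in how a component of the primary endpoint is decided, and it merits a change before lock. It is conditional. The flag can decide a level only when that level is at or near the minimum number of responders: 9.2% per level at the planned 50% rate, 18.6% at 40% and 21.4% at 33%, for 15 subjects. In a pump cohort one flag is then enough for about 72% of responders and two for the rest, assuming independent infusions at 61% validity. A disputed medication must also fall on a pivotal subject, and the documents give no rate for that.

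A reader might also infer that a subject flagged at one level is lost at every higher level. The documents do not support this. Moves to the next level are decided at office visits, while flags are set just before lock. Response is counted from valid infusions at each level. The exclusion of later data in Protocol 11.3.5 and SAP 11.2 concerns subjects who continue at a tolerated level after non-response, not subjects who had already moved up.

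Nothing here shows that the sponsor would decide unfairly. The point is that the plan does not show whether the decisions matter.

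**What to change.** 1. The sponsor reconciles Protocol 7.2, Protocol 7.3 and the SAP 11.1 list, and states which prevails where they overlap. Which medications to allow is the sponsor's decision.
2. In SAP 11.1, set the flag by program from a pre-specified coded medication list and the plan's own 12 h window wherever times are recorded. SAP 9.4 already plans WHO drug coding with ATC classes, and a listing with start and end dates and times.
3. A code list cannot settle purpose, and some times or dates will be missing. Settle those cases before lock on a file without cohort, level, validity and responder status, and record the reason for each.
4. Report the responder rate for each cohort and level with and without the medication flag.
5. State how a flag set before lock is treated for a subject who has already moved to a higher level.

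The cost is a code list, fewer columns in a file already planned, a short coding and review step before lock, and one extra run of the responder table. The sample size does not change.

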### Definition of responder

For the Pump-Assisted Cohorts, a subject is considered as a ‘responder’ for a certain infusion parameter if he/she has performed  $\geq 3$  valid infusions for that infusion parameter in any order (i.e., not necessarily consecutive).

For the Manual Push Flow Rate Cohort, a subject is considered as a ‘responder’ for a certain infusion parameter if he/she has performed  $\geq k$  valid infusions for that infusion parameter in any order (i.e., not necessarily consecutive) during the 4 weeks planned for that infusion parameter level, where  $k$  is specified in [Table 3](#):

**Table 3: Responder requirements in Manual Push Flow Rate Cohort**

Manual push infusions per week	Total number of infusions scheduled for parameter set	Minimum number of valid infusions ( $k$ )
2	8	5
3	12	7
4	16	10
5	20	12
6	24	15
7	28	17

Rationale for number of valid infusions to qualify a responder in the Manual Push Flow Rate Cohort: The probability for a subject to be a responder for a certain infusion parameter is assumed to be 50% irrespective of the value of the infusion parameter itself, i.e. identical to the assumed response rate in Clinical Study Protocol Section 11.1. This assumption is based on the expectation that there will be no infusion-related reasons for a subject to interrupt the infusion or change the infusion parameters. To achieve  $\geq 3$  out of 4 valid infusions the probability for a single infusion to be valid has to be  $\geq 61\%$  for Pump-Assisted Cohorts. Using this 61% success probability for a single infusion in the Manual Push Flow Rate Cohort the minimum number of successes (k) in Table 3 corresponds to a probability for a subject to be a responder of at least 50%.

**Calculation of percentage of responder**

The percentage of subjects with response  $R_{c,p}$  in cohort  $c$  to a certain infusion parameter  $p$ ,  $R_{c,p}$ , will be calculated as:

$$R_{c,p}(\%) = \frac{100 * (\text{Number of responder for } p \text{ in cohort } c)}{\text{Number of subjects in the SAF for cohort } c}$$

where response is defined as outlined above.

The success criterion for any  $R_{c,p}$  will be considered fulfilled if  $R_{c,p} \geq 33\%$ .

Within each cohort, the highest infusion parameter with fulfilled success criterion will be considered the new top infusion parameter to be recommended for the Hizentra® label. No formal statistical testing will be performed.

All subjects included in the SAF of a cohort will be included in the denominator for calculation of  $R_{c,p}$ .

Number of infusions and number and percentage of valid infusions and number and percentage of responder will be presented by cohort and infusion parameter level. The base for the percentages will be the number of infusions and the number of subjects within the cohort.

Subgroup analyses for

- Age class ( $\leq 17$  years,  $> 17$  years) and
- BMI class ( $< 30$  kg/m^2,  $\geq 30$  kg/m^2)

will be produced (Table 14.3.2).

A by-subject listing with the information as described in Section 7 as well as start and end date and time of infusion, depending on the cohort and planned infusion parameter level: actual parameter level and percentage of planned and for manual push actual infusion duration and calculated infusion duration, for all cohorts: infusion interrupted or stopped, prohibited concomitant medication administered, validity of the infusion, and responder (no/yes) will be provided. In this listing, the data which is collected after a subject has been classified as non-responder will be flagged.

## 11.2 Non-Responder

If a subject is unable to tolerate a certain infusion parameter level (i.e., is a non-responder at that level), the subject will continue study participation at the highest individually tolerable infusion parameter level for the remaining full study duration to collect safety information.

If a subject is a non-responder at a certain infusion parameter level, data collected until the time of non-response will be taken into account for the analysis of response. Data collected at the individually tolerable infusion parameter level after the non-response in the subjects will not be included in the analysis of response but will be listed and flagged in the listing.

The start date of non-response is the start date of the next infusion after the subject has been classified as non-responder. If a subject is a non-responder at the last infusion parameter level, the start date of non-response will be missing as no further data will be collected after the last infusion parameter level.

### 11.3 Extent of Exposure

Actual dose in mg/kg will be taken as entered in the database. For the Manual Push Flow Rate Cohort, the planned weekly volume will be derived from the planned weekly dose as entered in the eCRF assuming the nominal IgG content of IgPro20 being 200 mg/mL:

planned volume (mL) = planned dose (mg/kg) \* body weight (kg) / 200 mg/mL.

Subject's duration of exposure (days) in each infusion parameter level will be calculated as

(minimum of (treatment end date in parameter level [i] + 7 days, treatment start date in parameter level [i+1] – 1 day, study completion date) – treatment start date in parameter level [i]) + 1.

Subject's overall duration of exposure (days) will be calculated as

study completion date – date of first treatment + 1.

Duration in weeks will be derived by dividing the above item by 7.

Descriptive statistics for duration of exposure in weeks for each infusion parameter level and overall will be presented. In addition, the subject-years of exposure for each infusion parameter level and cohort will be given.

Subject's prescribed and actual dose (mg/kg) and total planned and actual volume (mL) per week will be summarized descriptively by cohort and infusion parameter level.

Number and percentage of incomplete infusions or infusions stopped will be presented. The base for the percentage will be the total number of infusions within the cohort.

### 11.4 AEs

AEs starting on or after the date (and time if available) of the first administration of study treatment will be considered treatment-emergent AEs (TEAEs). This is the formal definition of a TEAE. It should be kept in mind that all subjects have been on a stable Hizentra® dose prior to study start.

When the AE start date is missing or partially missing, AEs will be assumed to be treatment-emergent, unless there is clear evidence (through comparison of partial dates) to suggest that the AE started prior to the first dose of study treatment. For the assignment of AEs within 72 hours after administration of treatment (temporally associated AEs), only AEs

with complete start dates will be considered. The start time will also be considered if available. AEs which start during infusion or within 72 hours after the end of an infusion will be considered temporally associated AEs.

Only TEAEs occurring until EOS visit will be included in the summary tables. All AEs will be listed.

For non-responder subjects at a certain infusion parameter level, AEs reported at the individually tolerable infusion parameter level after the non-response in the subject, i.e., AEs starting at or after the next infusion following the infusion leading to non-response, will be listed and flagged. These AEs will be analyzed separately from the AEs reported prior to that time.

AEs will be coded using the MedDRA version 20.0 or higher. AEs will be primarily classified by MedDRA PT. Analyses will be performed by SOC and PT. Aggregated incidences at SOC level and Any TEAE will also be provided.

Summaries of TEAEs will count the number of subjects, that is, subjects with multiple occurrences of the same PT will be counted once. Summaries of TEAEs will also include the number of events for each PT. Summaries will be presented for each infusion parameter and total within cohort. TEAEs will be assigned to the infusion parameter level under which they occurred. In the Total column within cohort, each subject will only be counted once with all events experienced.

AE rates per infusion will be calculated within cohort in the following way for each infusion parameter level:

- $$\text{AE Rate per Infusion} = \frac{\text{Number of Events for a Particular PT}}{\text{Number of Infusions}}$$

where number of infusions will be the sum of all infusions that subjects received within infusion parameter level irrespective of their validity as defined in Section 11.1.

Each AE summary table will present the number of subjects, percentage of subjects based on the SAF, number of events, and AE rate per infusion.

One overview summary of TEAEs table with entries for:

- any TEAE;

- causally related TEAEs;
- temporally associated TEAEs within 72 h;
- causally related or temporally associated TEAEs within 72 h
- deaths;
- causally related deaths;
- serious TEAEs;
- causally related serious TEAEs;
- study discontinuation due to TEAE;
- causally related study discontinuation due to TEAE;
- study drug withdrawal due to TEAE;
- causally related study drug withdrawal due to TEAE;
- local TEAEs;
- causally related local TEAEs;
- maximum severity of TEAEs.

will be produced.

The following summary tables of TEAEs will be produced:

- by SOC and PT;
- SAEs by SOC and PT;
- by SOC, PT, and maximum severity (missing severity will be presented as separate category);
- by SOC, PT, and causality (missing causality will be considered “Related” as outlined in Section [8.1.1](#));
- by SOC and PT temporally associated within 72 hours after treatment;
- by SOC and PT causally related or temporally associated within 72 hours after treatment;

- time to onset of TEAEs (descriptive statistics and categories 0 days, 1 day, 2 days, 3 days, > 3 days);
- duration of TEAEs (descriptive statistics and categories 1 day, 2 days, 3 days, > 3 days);
- tolerability of the infusion parameter (number of infusions without severe local reactions / number of all infusions).

Time to onset of TEAE will be calculated as

TEAE start date and time – infusion start date and time.

For the categories, the time will be rounded to days.

Duration of TEAEs will be calculated as defined in Section 8.2.3.

Tolerability of a certain infusion parameter within a cohort will be calculated as

number of infusions without severe local reactions / number of infusions

and will be presented by infusion parameter and cohort. The number of infusions irrespective of their validity as defined in Section 11.1 will be used as denominator for the assessment of tolerability. The total number of infusions within infusion parameter level and within cohort will be considered as denominator for the tolerability within infusion parameter level and within cohort, respectively. An infusion without severe local reactions is defined as no occurrence of a severe local reaction from the start date and time of an infusion until the start date and time of the next infusion or study end if this was the last infusion.

Local TEAEs will be identified by the MedDRA high level terms “administration site reactions NEC”, “infusion site reactions”, and “injection site reactions”. The MedDRA high level terms will be reviewed prior to database lock and the list of terms to be included into Local TEAEs will be updated. Local TEAEs will be included in all tables by using a virtual SOC called “Local Adverse Events”. In addition, the local TEAEs will also be presented by their MedDRA SOC “General disorders and administration site conditions”.

TEAEs will be sorted in descending order of total incidence by SOC and PT.

The summary will report for the Any TEAE row, each SOC, and each PT, the number of subjects with at least one TEAE, counted for the maximum reported severity in the table by severity. Local TEAEs will be reported only once in the Any row.

A listing of MedDRA SOC, PT, and verbatim text will be provided.

All AEs will be listed. TEAEs will be listed for the SAF. Other AE listings will use all available data. The listings will include the variables as specified in Section 7 and in addition MedDRA SOC, PT, and the verbatim, AE start and end date and time if available, duration of AE in days, severity, serious (yes or no), relationship to treatment (yes or no), outcome, action taken, and AE flags (TEAE, SAE, temporal relationship within 72h [AE72h]). Additionally, a listing of subject IDs for each individual PT will be produced.

The following listings will be provided:

- Non-TEAEs – all available data;
- TEAEs – SAF;
- Deaths – all available data;
- SAEs – all available data;
- AEs leading to study discontinuation – all available data;
- Local TEAEs – SAF;
- MedDRA SOC and PT with all AE verbatim – all available data;
- Subject IDs for each PT – all available data.

In all listings, the data which is collected after a subject has been classified as non-responder will be flagged.

